15.6 HYPOTHESES

As this is a descriptive study no specific hypotheses have

15.7 STUDY TWO PARTICIPANT ELIGIBILITY CRITERIA

15.7.1 INCLUSION CRITERIA

Participants meeting the following inclusion criteria will be invited to participate in the study (see 15.1);

- Over 18 years of age
- Able to read and speak English
- A clinician currently practicing in the fields of medicine, nursing or allied health

15.7.2 EXCLUSION CRITERIA

Participants will be excluded from the study for the following reasons (see 15.1);

- Under 18 years of age
- Not currently registered with Australia Health Practitioner Regulation Association

15.8 RECRUITMENT

The survey population will be recruited from The Brisbane Private Hospital. A link to complete the survey will be emailed through existing email lists associated with BHULRI.

15.9 SAMPLE SIZE

As this is a descriptive study examining practicing clinicians perspectives of POCD no power analyses can be conducted.

16 SCREENING /ENROLMENT

Patients will be screened according to the selection criteria. Those who meet the selection criteria will be invited to complete the survey. After reviewing the Participant Information form (24.7) and acknowledging that they have understood the purpose of the study, their involvement, risks and benefits. Any participant who refrains from participation will not be disadvantaged in any way.

17 DATA COLLECTION

17.1 DATA COLLECTION FOR PRIMARY AND SECONDARY OUTCOMES

Demographic data and survey data will be completed by each participant on an online database QUALTRICS.

17.1.1 DEMOGRAPHIC AND MEDICAL INFORMATION FORM

Demographic information will be obtained from each participant who agrees to participate in the survey. This information will include, but is not limited to:

- Age
- Gender
- State
- Profession
- Level within that profession
- Years in Clinical Practice
- Client groups the participant works with (e.g. adult internal medicine, geriatric neurology)
- Based in hospitals (e.g. public or private) or private practice.

18 OUTCOME MEASURES

18.1 SURVEY

A survey has been designed and developed on Qualtrics to examine each individual clinician's experiences of POCD in practice (24.6). The participant information sheet and consent form will be provided online at the beginning of the survey (24.7 & 24.8). The questions will identify whether each individual clinician has encountered POCD or not in practice. If they have encountered POCD in clinical practice follow up examination includes how many times they have encountered POCD, what cognitive functions were effected, the duration of POCD, were there any emotional symptoms, how it was managed and what else could have been done to manage POCD. If they have not previously encountered POCD in clinical practice follow up examination includes what cognitive functions they expect to be effected, would they expect emotional symptoms and how they might manage a patient experiencing POCD. The survey is expected to take 10 minutes to complete.

19 CONFIDENTIALITY

Information about study subjects will be kept confidential and managed accordingly to the requirement of Human Research as determined by the NHMRC, and the local ethics review board, in this case, the Bellberry Human Research Ethics Committee.

All data will be downloaded in non-identifiable format from the Qualtrics Database and stored on securely on electronically on password-protected computers by the research team based at the Brisbane Hand and Upper Limb Research Institute, for purposes of analysis.

20 DATA ANALYSIS

Data will be downloaded directly from Qualtrics into an SPSS datasheet. Analysis will be performed with the assistance of a statistician and the statistical package used will be SPSS.

20.1 STATISTICAL METHODS

As this is a descriptive study, demographic data and outcome variables will be examined using descriptive statistics (means, standard deviations [SDs], and percentages).

21 RISK ANALYSIS

This is a low risk study with no foreseeable risks.

22 BUDGET AND FUNDING IN-KIND SUPPORT

	Item	Source	Details	Costs to BHULRI & UQ
1	Investigator time & Research assistant	BHULRI & UQ	Protocol development, ethics, data entry, analysis, writing paper for publication, submission.	In Kind

23 DISSEMINATION

Dissemination will be the same as study one (13).

24.1 Eligibility Checklist

Does the patient meet the following inclusion criteria?

1. Able to read and speak English
2. Over 18 years of age
3. Requires shoulder surgery in the Beach Chair position

Does the patient have any other clinical characteristics requiring exclusion from the study?

Exclusion Criteria	Yes	No
Under 18 years of age		
Pre- operative Mini-Mental State Examination (MMSE) < 24		
Pre-existing Cerebrovascular Disease		
Orthostatic hypotension		
ASA physical status IV and V*		
History of drug and/or alcohol abuse		
Unstable mental health condition		
Neurological disease (e.g. previous stroke)		
Currently pregnant or suspected to be pregnant		

ASA = the American Society of Anaesthesiologists physical status classification system. Level IV indicates the presence of severe systemic disease that is a threat to life. Level V is a moribund person who is not expected to survive without some form of surgery.

24.1.1 PARTICIPANT ELIGIBILITY CRITERIA

INCLUSION CRITERIA

Patients meeting the following inclusion criteria will be invited to participate in the study (see 14.1);

- Have a shoulder condition for which surgery in the BCP is appropriate.
- Over 18 years of age
- Able to read and speak English

EXCLUSION CRITERIA

Patients will be excluded from the study for the following reasons (see 14.1);

- Under 18 years of age
- Pregnant women
- Pre- operative Mini-Mental State Examination (MMSE) < 24

- Pre-existing cerebrovascular disease as reported by the assessing medical consultant and recorded in patient charts
- Orthostatic hypotension
- ASA physical status IV and V*
- History of drug and/or alcohol abuse
- Neurological disease (e.g. previous stroke)
- Significant mood and anxiety disorders as determined by treating consultant
- Any other condition, which in the opinion of the investigators, would render the patient unsuitable for participation in the study

* ASA = the American Society of Anaesthesiologists physical status classification system. Level IV indicates the presence of severe systemic disease that is a threat to life. Level V is a moribund person who is not expected to survive without some form of surgery.

Anaesthetic medication	
What medications were used during surgery and what doses were given?
 
1.
 
2.
 
3.
 
4.

Intraoperative Drug Record	
What medications (other than anaesthetics) were used during the surgery and what doses were given?
 
1.
 
2.
 
3.

	4.
Perioperative Drug Record	
What medications (other than anaesthetics) were provided before and/or after the surgery and what doses were given?
 
1.
 
2.
 
3.
 
4.

Post -Operative Record	
Analgesic Protocol	Medications used:-
Nausea	Yes  No 
Vomiting	Yes  No  Frequency _____
Length of Hospital Stay	

INVESTIGATOR SIGNATURE

24.6 Participant Survey – STUDY TWO

HEALTH PROFESSIONALS' EXPERIENCES OF POST OPERATIVE COGNITIVE DECLINE

PROFESSIONAL BACKGROUND

The following questions are about you and your profession.

Age: _____

Gender:

Male

Female

State:

Queensland

New South Wales

Victoria

South Australia

Canberra

Western Australia

Tasmania

Other:

What is your profession?

Medical

Area: _____

Nursing

Psychology

Neuropsychology

Occupational Therapy

Speech Pathology

Physiotherapy

Other

What level are you currently in your profession? _____ (e.g. interns, registrar, fellow, professor)

How senior is your position in your current organization:

Very senior

Senior

Intermediate

Junior

Very junior

How many years have you been in clinical practice (years)?

≤1

1-3

4-7

8-10

≥10

How long have you worked for your *current* organisation? _____ (weeks/months/years)

Who is your employer?

- Public Sector
- Private Sector
- Private Practice
- University
- Multiple

What population(s) do you currently work with?

- Paediatric
- Adult
- Geriatric

In which areas (e.g. surgical, neurology, internal medicine, allied health): _____

Postoperative cognitive dysfunction (POCD) is a decline in cognitive function more typically seen after a few days to several months following surgery, but can last for several years.. It is distinct from delirium, which only occurs within the first few days. The decline in cognitive function is not attributed to any adverse complications and occurs peri-operatively. What we would like to know is your experiences of POCD in a *clinical setting*.

1. Have you encountered POCD before?

- YES
- NO

If you answered yes please complete questions 2 to 9. If you answered no please go to question 10.

2. How many times have you encountered it? _____ (number)

3. What cognitive functions were impacted? If you have seen more than one case of POCD, identify all the areas that were affected across the people you have seen:

- Short Term Memory
- Long Term Memory
- Attention/ Working Memory
- Planning/Organisation
- Inhibition
- Initiation
- Self-monitoring
- Emotional Control
- Gross and Fine Motor Control
- Language
- Learning

4. For the problems you identified, please number them in order of the general impact you felt this had on the person's (or people, if you have encountered more than one case) everyday functioning from 1= least impactful to 5 = most impactful.

- Short Term Memory
- Long Term Memory
- Attention/ Working Memory
- Planning/Organisation
- Inhibition
- Initiation
- Self-monitoring
- Emotional Control

- Gross and Fine Motor Control
- Language
- Learning
- 5. How long did the POCD last?
- 3-7 days
- 8-28 days
- 4-6 weeks
- 6 weeks to 3 months
- >3 months
- >12 months
- Unknown

6. Did people experience any associated emotional changes? Please tick all that apply

- Low mood
- Nervousness/Worry
- Panic
- Stress
- Fatigue
- Change in sleep
- Irritability
- Weight gain/loss
- Change in appetite
- Excessive crying
- Poor concentration
- Restlessness
- None

7. How was the POCD and/or emotional changes managed?

- No additional intervention to treatment-as-usual
- It was monitored
- Assessment
 - Brief screen (e.g. MMSE)
 - Full Cognitive Battery
- Referral
 - Clinical Psychologist
 - Neuropsychologist
 - Speech Therapist
 - Occupational Therapist
 - Neurologist
 - Other professional
- Other: _____

8. In your opinion could anything else have been done to manage the cognitive and/or mood symptoms? _____

9. If you have any additional information you would like to share about POCD or to provide comments on the survey, please do so here. _____

10. Given the nature of POCD as described above, what cognitive functions do you feel might be vulnerable? Please rank these in order from the 1=most likely to 5= least likely:

- Short Term Memory
- Long Term Memory
- Attention/ Working Memory
- Planning/Organisation
- Inhibition
- Initiation
- Self-monitoring
- Emotional Control
- Gross and Fine Motor Control
- Language
- Learning

11. Would you anticipate changes to emotional functioning? If so, what might you expect to see? Please rank these in order from the 1=most likely to 5= least likely

- Low mood
- Nervousness/Worry
- Panic
- Stress
- Fatigue
- Change in sleep
- Irritability
- Weight gain/loss
- Change in appetite
- Excessive crying
- Poor concentration
- Restlessness
- None

12. In your opinion, how do you feel POCD should be managed?

- No additional intervention to treatment-as-usual
 - Monitor the POCD
 - Provide Assessment
 - Brief screen (e.g. MMSE)
 - Full Cognitive Battery
 - Further Referral
 - Clinical Psychologist
 - Neuropsychologist
 - Speech Therapist
 - Occupational Therapist
 - Neurologist
 - Other professional
- Other: _____

9. Any other comments _____

Thank you for your participation. If you would like to know the outcome of the survey please email [contact] otherwise a summary of results from the study will be finalized and published on our website (www.upperlimb.com) in 2019.

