15.5 RESEARCH QUESTIONS

STUDY TWO has five research questions, based on the perspective of practicing clinicians;

- (i) How many times has POCD been seen in a clinical setting?
- (ii) How often are psychological symptoms seen comorbidly with POCD?
- (iii) How POCD is currently managed in clinical practice?
- (iv) What are clinician perspectives on how POCD should be managed?
- (v) Does the experience of POCD differ between professions and clinical populations?

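### The only structured survey item on how POCD should be managed (Study Two, question 12) is never put to clinicians who have encountered POCD

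*Protocol*

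**What the plan says.** Protocol section 15.5 lists five research questions for Study Two, all from the perspective of practising clinicians. Question (iii) concerns present practice: "How POCD is currently managed in clinical practice". Question (iv) concerns opinion: "What are clinician perspectives on how POCD should be managed". Neither is limited to clinicians with, or without, experience of the condition.

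The survey in section 24.6 opens its clinical part with a yes/no filter, "Have you encountered POCD before", followed by the routing instruction "If you answered yes please complete questions 2 to 9. If you answered no please go to question 10".

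- On the yes branch, question 7 asks "How was the POCD and/or emotional changes managed" with a tick-list. Question 8 asks in free text "In your opinion could anything else have been done to manage the cognitive and/or mood symptoms". Question 9 is an open comment.
- On the no branch, question 12 asks "In your opinion, how do you feel POCD should be managed" with a tick-list.

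Section 18.1 describes the same two tracks. It gives experienced clinicians the items on what was done and what more could have been done. For the others it says "If they have not previously encountered POCD in clinical practice follow up examination includes what cognitive functions they expect to be effected", and goes on to emotional symptoms and how they might manage a patient. Section 14 lists factors in the same paired form. Section 20.1 plans descriptive statistics only: means, standard deviations and percentages.

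**The concern.** The item that puts research question (iv) almost word for word is withheld from the respondents who have seen the condition. If (iv) is summarised with the planned percentages, those percentages describe opinion among clinicians who have not encountered POCD, whereas the question is about clinicians in general.

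The experienced group is asked something narrower, in a different format. Its views cannot be added to the question 12 figures or compared with them. This is settled when the data are collected: no later analysis can supply question 12 answers that were never requested.

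**Working it through.** The protocol states no sample-size or precision figure for Study Two (section 15.9 says no power analysis can be done), so there is no figure to reproduce. The check is a trace of the routing, followed by an illustration of the counts.

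**Step 1. Trace the branches (section 24.6).**

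| Answer to question 1 | Items reached | Items bearing on management |
|---|---|---|
| Yes | 2 to 9, then stop | 7 (what was done), 8 (what more could have been done), 9 (comment) |
| No | 10, 11, 12, comment | 12 (what should be done) |

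The closing comment item on the no branch is also numbered 9. This is a numbering slip and does not bring yes respondents to question 12.

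**Step 2. Compare the two opinion items.**

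| | Question 8 (yes branch) | Question 12 (no branch) |
|---|---|---|
| Format | Free text | Closed list plus other |
| Refers to | Cases already seen | POCD in general |
| Scope | Additions to what was done | Any option, including nothing beyond usual treatment |
| Symptoms named | Cognitive and/or mood | POCD |

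A respondent who thinks a step taken was right, or was unnecessary, has no prompt in question 8 to say so. Percentages can be read straight from question 12. From question 8 they first need a coding scheme, and even then they measure something different.

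**Step 3. Compare questions 7 and 12.** The option lists are nearly the same: no addition to usual treatment, monitoring, assessment by brief screen or full battery, referral to the same professions, and other. The main difference is that question 7 also covers emotional changes. The survey thus already holds near-matching lists for what was done and what should be done, but the routing gives them to two groups that do not overlap. Any difference between them is mixed with the difference between having and not having encountered POCD.

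**Step 4. Count who answers question 12.** Let N = 200 (section 14, approximate) and let e be the share who have encountered POCD. The protocol does not give e, so the values below are assumptions. Answers to question 12 = N × (1 − e). The 95% half-width at an observed 50% = 1.96 × √(0.25/n).

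| e (assumed) | n answering question 12 | Of whom have encountered POCD | Half-width |
|---|---|---|---|
| 25% | 200 × 0.75 = 150 | 0 | 8.0 points |
| 50% | 200 × 0.50 = 100 | 0 | 9.8 points |
| 75% | 200 × 0.25 = 50 | 0 | 13.9 points |
| Any, with all routed to question 12 | 200 | 200 × e | 6.9 points |

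The loss of precision is secondary. The third column is the point: it is zero whatever e is.

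**The case against.** The strongest reply is that the split is deliberate. Sections 14, 18.1 and 24.6 agree with one another: clinicians who have met POCD report experience, and the rest report expectation. Question 8 asks the experienced group for an opinion on management, and section 14 lists the matching factor. No item is formally mapped to a research question, so question 8 could be coded and reported beside question 12. Study Two is descriptive, with no hypotheses and no power calculation.

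Much of this stands, and it rules out three stronger readings that a reader might infer.

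- *That (iv) is answered with no input from experienced clinicians.* Questions 8 and 9 give some. The filter is also on having encountered POCD, not on having managed it, so it is inexact to say that those who have managed it are excluded.
- *That the gap between actual and preferred management cannot be seen within any respondent.* Questions 7 and 8 together give a partial view for the yes branch, in free text and limited to additions.
- *That the study's purpose depends on comparing current with preferred management.* Section 15.2 states the purpose as gaining clinicians' perspectives and learning what is encountered and done. It names no such comparison, and the only comparative research question, (v), is about professions and clinical populations.

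The reply does not show that question 8 can stand in for question 12. Intended symmetry does not settle it either. Sections 14 and 18.1 describe the no-branch item as what clinicians would expect or might do, which is the hypothetical partner of question 7. Question 12 as printed asks what should be done, which is research question (iv) itself, and that question is not confined to one branch.

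**Conclusion.** The point holds in a limited form. As the survey is written, no clinician who has encountered POCD reaches the only structured item on research question (iv). That group's contribution to (iv) is free text about additions to past management, plus any open comment. The two groups therefore cannot be pooled or compared on one item, and the summaries in section 20.1 apply directly to (iv) only for clinicians without experience.

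The routing result rests on the printed instruction alone and assumes that the online version follows it. The counts of 150 to 50 rest on an assumed 25% to 75% having encountered POCD. The effect is confined to one of the five Study Two research questions and is partial even there. Study One, including its primary outcome, is unaffected. It is worth correcting because the correction is cheap and the missing answers cannot be recovered at analysis.

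**What to change.** 1. In section 24.6, keep question 8 and change the routing so that a yes leads to questions 2 to 9 and then question 12, and a no leads to questions 10 to 12. Renumber the closing comment item on the no branch, which now repeats the number 9.
2. Amend section 18.1 so that the question on how POCD should be managed is described as put to all respondents.
3. Report question 12 overall and by whether POCD has been encountered. Among clinicians who have encountered it, set question 7 beside question 12, noting that question 7 also covers emotional changes.

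The cost is a change to the online skip logic, a short edit to section 18.1, and one more tick-list item, likely under a minute, for yes respondents. That group would answer question 12 after recalling its own cases, so the comparison by experience should be read with that in mind.

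If responses have already been collected under the present routing, the fallback is to state that (iv) is informed by question 8 for those who have encountered POCD and by question 12 for those who have not. The two should then be reported separately, with no pooled percentage. This costs nothing in data collection but leaves the two groups without a common item.

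### Study Two survey: question 7 pools management of POCD with management of emotional changes, so for clinicians who report emotional changes the answer cannot be attributed to POCD

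*Protocol*

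**What the plan says.** Protocol section 15.5 lists five research questions for Study Two. Two matter here: (ii) "How often are psychological symptoms seen comorbidly with POCD" and (iii) "How POCD is currently managed in clinical practice". Section 18.1 describes the survey in the same terms: emotional symptoms are one topic, and the management of POCD is another.

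The survey itself is in section 24.6. For clinicians who have encountered POCD, the relevant items are:

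- Question 3 lists the cognitive functions affected. "Attention/ Working Memory" is one of them.
- Question 6 asks "Did people experience any associated emotional changes? Please tick all that apply". It offers twelve symptoms, including "Poor concentration", plus a 'None' option.
- Question 7 asks "How was the POCD and/or emotional changes managed". It has a single option list covering no additional intervention, monitoring, assessment and referral, the last including referral to a clinical psychologist.
- Question 8, free text, asks "In your opinion could anything else have been done to manage the cognitive and/or mood symptoms".

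Clinicians who have not encountered POCD skip to question 10. Their management item, question 12, names POCD only: "In your opinion, how do you feel POCD should be managed".

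The analysis (section 20.1) is descriptive: means, standard deviations and percentages.

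**The concern.** Research question (iii) is about POCD. Question 7 is about POCD, emotional changes, or both, and the respondent has no way to say which. A clinician who referred a patient to a psychologist because of low mood, and did nothing further about the cognitive decline, ticks the same box as one who made the referral because of the decline. If the result is published as how POCD is managed, practice may look more active than it is. No analysis plan can put this right, because the attribution is never collected.

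The second strand concerns research question (ii). Concentration appears among the emotional changes in question 6, while attention is a cognitive function in question 3. Study One treats concentration as cognition too: section 8.1.1 describes Letter-Number Sequencing as a test of attention and concentration, and that test belongs to the battery that defines POCD. A clinician who saw only cognitive effects could therefore be counted as having seen an accompanying emotional change.

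**Working it through.** The protocol states no figure for either point, so there is nothing to reproduce. The check sets the items against the research questions and then derives what the collected answers can and cannot bound.

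**Step 1: item against target.**

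| Target | Item meant to answer it | What the item covers |
|---|---|---|
| Research question (iii): current management of POCD | Question 7 | POCD and/or emotional changes, one option list |
| What else could have been done for POCD (section 18.1) | Question 8 | Cognitive and/or mood symptoms, free text |
| Research question (ii): psychological symptoms alongside POCD | Question 6 | Twelve symptoms, one of which overlaps a function in question 3 |

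No other structured item asks clinicians who have seen POCD what was actually done.

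**Step 2: what question 7 identifies.** Let N be the number of clinicians in the branch that has seen POCD. For a given active option (for example, referral to a clinical psychologist), let:

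- a0 = number who tick it and ticked 'None' in question 6;
- a1 = number who tick it and reported at least one emotional change in question 6.

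The observed share is (a0 + a1)/N. For the a0 group there was no emotional change to manage, so the action must concern POCD. For the a1 group the target is unknown. The share who used the action for POCD therefore lies in

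a0/N ≤ true share ≤ (a0 + a1)/N.

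The possible overstatement runs from 0 to a1/N. The documents give no value for a0 or a1, so it cannot be narrowed further. The upper limit assumes that respondents may tick every option that applies; question 7, unlike question 6, carries no instruction on this. The argument covers the active options, not the option of no additional intervention.

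**Step 3: what 'Poor concentration' can do to question 6.** Let p12 be the share ticking at least one of the twelve symptoms, and p11 the share ticking at least one of the other eleven (12 − 1 = 11). Then

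p12 − p11 = s,

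where s is the share whose only tick is 'Poor concentration'. A clinician who ticks it together with, say, low mood is counted in both p12 and p11, so the overlap changes nothing for that clinician. The value s lies between 0 and the share ticking the item at all. The documents give no figure, but s can be computed from the data because question 6 offers each symptom as its own tick-box.

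**Step 4: routing.** Section 24.6 sends clinicians who have seen POCD to questions 2 to 9 and the others to question 10 onward. Nobody is routed to both question 7 and question 12.

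**The case against.** The best defence of question 7 is the stated purpose. Section 15.2 says the survey is to learn what is done about POCD and about its possible psychological consequences, and the joint wording of questions 7 and 8 follows that. This shows the wording is deliberate. It does not make the item adequate: if both targets matter, each needs its own answer, and a pooled percentage reports neither.

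A second defence is that much can be recovered at analysis. This is right for question 6, where the overlapping item can simply be left out. It is right for question 7 only among those who ticked 'None', and they are a selected and possibly small group: clinicians who recall no emotional change in the cases they saw.

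A reader might infer four stronger things, and the documents do not support them.

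- *That POCD management and psychological symptoms cannot be separated at all.* Emotional changes have their own tick-all item, and question 7 is unambiguous for the 'None' group.
- *That a clinician who saw impaired attention will also be counted as having seen psychological symptoms.* Question 6 asks about associated emotional changes, so nobody has to tick concentration there. Section 8.1.2 notes that distress affects cognitive performance, so listing concentration as an accompaniment of distress is not plainly wrong.
- *That research question (ii) is biased in a known direction.* Question 3 lists emotional control among the cognitive functions, so the overlap also runs the other way.
- *That the wording of question 7 spoils a comparison of current with preferred management in question 12.* Given the routing, that comparison is between different clinicians however question 7 is worded.

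**Conclusion.** The point holds in a limited form. Among respondents who report any emotional change in question 6, an action ticked in question 7 cannot be attributed to POCD, to the emotional change, or to both. A percentage presented as POCD management can then exceed the true share by anything from 0 to a1/N, assuming that all applicable options may be ticked and that answers to question 6 are accurate. Question 8 has the same limitation.

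'Poor concentration' is a minor overlap. It can raise a crude any-emotional-change percentage by exactly the share for whom it is the sole tick. The protocol does not define such a summary, so this is a caution about reporting rather than an error in a stated analysis.

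The consequence is modest. Study Two is a descriptive survey with no hypotheses and no power calculation, and nothing in Study One's outcome, sample size or analysis is touched. This is a cheap improvement that lets the survey answer its own research question.

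**What to change.** **If the survey can still be changed**

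- Split question 7 into 7a (cognitive decline) and 7b (emotional changes), with the same option list for both. Ideally split question 8 the same way.
- Leave 'Poor concentration' out of the emotional-change summary, or report that summary with and without it. Question 11 carries the same item and should be handled consistently.

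**If responses are already in**

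- Label question 7 in every table as management of POCD and/or emotional changes, and label the question 8 answers as joint too.
- Show respondents who ticked 'None' in question 6 separately, as a sensitivity result in a selected subgroup and not as the main estimate.
- Report question 6 with and without 'Poor concentration'.

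**In either case**

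- Label any comparison with question 12 as one between different respondents.

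**Cost.** One or two extra items, estimated at half a minute per respondent. Against the 10 minutes expected in section 18.1, that is 0.5/10 = 5% more time. After data collection the cost is relabelling and one filter. The sample size does not change.

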14 CLINICAL INVESTIGATION PLAN SUMMARY- PART TWO

TITLE	Health professionals' experiences of post-operative cognitive decline
INVESTIGATORS	Principal: Associate [name], [name], [name], [name] Associate: [name], [name], [name], [name], [name]
OBJECTIVES	The general aim of the study is to understand what professionals experience and understand of POCD, and/or what they might expect to experience.
STUDY DESIGN	Descriptive Survey
SITES	Brisbane Private Hospital
NUMBER OF SUBJECTS	Approximately 200 participants will be recruited to this study.
TARGET POPULATION	Participants will be currently practicing medical, nursing and allied health practitioners.
LENGTH OF CLINICAL INVESTIGATION	It is anticipated that this study will require 6 months from commencement.
OUTCOME	Demographic data and outcome variables will be examined using descriptive statistics (means, standard deviations [SDs], and percentages). Factors examined will be: 
 • Whether each individual clinician has encountered POCD in practice • What cognitive functions were affected or what they would expect to see • The duration seen or expected • Whether there were any emotional symptoms or whether they would expect emotional symptoms • How it was managed or how they would expect it to be managed • What else could be done to manage POCD

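### Study Two survey, questions 10 and 11: clinicians must put 11 and 13 options in order using only the numbers 1 to 5, so the expected functions and emotional changes are not cleanly recorded

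*Protocol*

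**What the plan says.** Section 24.6 routes respondents by whether they have met POCD. Those who have answer questions 2 to 9; those who have not go to question 10.

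- **Have met POCD.** They tick the functions affected (question 3), then number only those by impact: "For the problems you identified, please number them in order of the general impact you felt this had", "from 1= least impactful to 5 = most impactful". Emotional changes (question 6) are a multiple-tick list with no numbers.
- **Have not met POCD.** There is no tick list for functions or emotional changes. Question 10 asks "what cognitive functions do you feel might be vulnerable? Please rank these in order from the 1=most likely to 5= least likely" and lists 11 functions. Question 11 opens by asking whether emotional change is anticipated and, if it is, what form it would take, and continues "Please rank these in order from the 1=most likely to 5= least likely". It lists 12 symptoms plus *None*.

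Section 14 counts among its six outcome factors "What cognitive functions were affected or what they would expect to see", and also whether emotional symptoms were present or would be expected. Section 18.1 repeats both. Section 20.1 plans means, standard deviations and percentages for the demographic and outcome variables together, without assigning a statistic to any item.

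**The concern.** An instruction to put items in order calls for as many distinct positions as there are items. Here there are five numbers for 11 and for 13 items, with no rule on ties, blanks or numbers above 5. Respondents must choose their own reading, and different people will choose differently.

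At stake are two stated outcome factors in the group that has not met POCD: which functions these clinicians expect to be affected, and whether they expect emotional change. Questions 10 and 11 are the only items that supply them. Someone who expects no emotional change might number *None* as 1, leave the whole item blank, or give every symptom a 5. These three records look different but mean the same. An analysis plan cannot repair this, because the defect is in what the instrument records and not in how it is summarised.

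**Working it through.** Study Two states no numerical result to reproduce. The check is a count, some rank arithmetic and one illustration.

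**Inputs (section 24.6).** Question 10 lists k = 11 functions; question 11 lists k = 13 options (12 symptoms plus *None*); the numbers offered are 1 to 5.

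**What each reading produces**

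| Reading | Items without a number | Average number given by one respondent |
|---|---|---|
| Top five, each number used once | k − 5: 11 − 5 = 6 (6/11 = 54.5%); 13 − 5 = 8 (8/13 = 61.5%) | (1+2+3+4+5)/5 = 3 |
| 1-5 rating, ties allowed | none need be blank | anywhere from 1 to 5 |
| Full ranking | none | (k + 1)/2: 6 for k = 11; 7 for k = 13 |

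The full ranking sits badly with 5 being labelled least likely, but it is what ordering the whole list would require.

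**Means.** For illustration, assume normally distributed opinions with SD 1, item means evenly spaced from +1.5 to −1.5, rating cut points at ±0.5 and ±1.5, and 100,000 respondents. None of these values comes from the protocol. The same opinions on 11 items then give:

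| Item | Full ranking | 1-5 rating | Top five (mean among those numbering it) |
|---|---|---|---|
| Most favoured | 2.61 | 1.68 | 2.19 (91% number it) |
| Least favoured | 9.38 | 4.32 | 4.20 (5% number it) |

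With 13 items the least favoured has 11.01, 4.31 and 4.18, the last from 3% of respondents.

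**Percentages.** These are not immune. Let a fraction f of respondents read question 10 as a top five and the rest number all 11 functions. The average share of functions given a number is f × 5/11 + (1 − f):

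- f = 0: 100%
- f = 0.5: 0.227 + 0.5 = 72.7%
- f = 1: 45.5%

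The figure depends on how the instruction was read, not on what was expected. Even if everyone used the top five, the count is capped at five per respondent, whereas the tick list in question 3 is not.

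**Can the readings be separated later?** Only in part. A number above 5 reveals a full ranking, and ties suggest a rating. A blank cannot be resolved: it may mean outside the top five, not expected, or skipped. Tied ratings cannot be turned into an order.

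**Yes/no part of question 11.** The question is conditional on an answer for which no field exists. *None* is the nearest substitute, but it stands in the list as one more option to be ranked.

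**The case against.** The strongest reply is that this is an appendix to a descriptive survey with no hypotheses, that the choice of statistic for each item belongs in an analysis plan, and that the online form may force one reading. Much of this stands. Section 20.1 does not assign means to these items, and leaving that choice open is no fault. None of the five research questions in section 15.5 asks which functions inexperienced clinicians expect; that appears only in sections 14 and 18.1. The online response control cannot be seen. But the wording printed in 24.6 fixes no reading, and no choice of statistic recovers what was not recorded.

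A reader might also infer stronger points that the protocol does not support:

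- **That reversed anchors make the results uninterpretable or impossible to compare.** In question 4 the strongest answer is 5, in question 10 it is 1. Each question prints its anchors, and if the answers are ratings, 6 − x aligns them. The reversal exists only between these two: the counterpart of question 11 is question 6, which has no scale. Question 4 measures impact and question 10 likelihood, so they would differ even with matching anchors, and no comparison of them is planned. The only comparison named in 15.5 is between professions and clinical populations.
- **That question 4 has the same defect.** It covers only the functions already ticked, so items outnumber the numbers only if more than five were ticked.
- **That 55% and 62% of answers will be missing.** Those shares hold only under the top-five reading.

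**Conclusion.** The point holds for questions 10 and 11. As printed, they request an ordering that five numbers cannot give and admit three readings that cannot be reliably separated afterwards. Up to 6 of 11 functions and 8 of 13 options are left without a number, or none are, depending on the respondent. Any mean or percentage of these items therefore lacks a single meaning, and two of the six factors in section 14 are not cleanly captured for clinicians who have not met POCD.

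The conclusion assumes that the online form follows the printed wording and does not itself enforce one reading. The simulated means are illustrative only; the counts are not. The scale direction in question 4 is a secondary matter of consistency. The consequence is confined to the descriptive Study Two and does not touch Study One.

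**What to change.** 1. **Questions 10 and 11.** Replace the ranking with multiple-tick lists in the format of questions 3 and 6. In question 11 make *None* an exclusive option, which also records the missing yes/no answer. Follow each list with a 1-5 rating of every ticked item, ties allowed.
2. **Question 4.** Ask respondents to rate each ticked function instead of numbering them in order, and use one scale direction (for example 1 = least, 5 = most) in all three questions.
3. **Section 20.1.** Add a sentence: report the percentage ticking each item, and the distribution of ratings among those who ticked it.
4. **Responses already collected.** Report answers given on the old wording separately.

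The cost is edits to three survey items and one sentence in 20.1. Any answers already given to the old questions cannot be pooled with the new ones.
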